The most common techniques used for canine retraction are sliding and loop mechanics which have been discussed frequently in literature.⁶ Both techniques possess their merits, encompassing advantages, such as minimal friction and precise manipulation of space closure using loops.⁷ Whereas, while using sliding mechanics, one can have the benefits of reduced wire bending time, control of arch form and root alignment.⁷ However, both of these methods have their limitations. With loop mechanics, the additional chair side time, skills, soft tissue irritation, root resorption, bacterial build up and uncontrolled tipping present a challenge.^{8,9} Friction and binding of wire to the bracket slot results in slow tooth movement and anchorage loss with sliding mechanics.⁹

Despite its limitations, sliding mechanics is a common technique used for canine retraction.¹⁰ The two widely used methods for sliding teeth include elastomeric power chains and Nickel-titanium (Ni-Ti) closed-coil springs.¹¹ Elastomeric power chains are extensively used in orthodontics because of their ease of use, effectiveness and patient comfort by allowing periods of regeneration.¹² Elastomeric power chains exert heavy intermittent forces when they return to their original length after being stretched, with decay of forces as they revert, requiring a greater number of appliance activation.¹³

On the other hand, Ni-Ti closed-coil springs apply light continuous forces and deliver a constant force over a period that lead to more efficient tooth movement and steadier space closure¹⁴, with reduced number of appliance activation.¹⁵ An in vitro study by Barsoum et al.¹⁶ reported a reduction in force with Ni-Ti closed-coil springs after 18 hours and remained constant for about

21 days. Badran et al.¹⁷ also found that Ni-Ti closed-coil springs were less tolerated than elastomeric power chains by patients but produced an average of 0.5 mm more tooth movement than the elastomeric power chain during the 12-week study period. Therefore, consideration of canine retraction with Ni-Ti closed-coil springs and elastomeric power chains is critical for enhancing the overall effectiveness of orthodontic treatment and to achieve desired treatment outcomes.

RATIONALE:

Premolar extraction followed by canine retraction is one of the common practices in orthodontics to treat malocclusion such as severe crowding and proclination of anterior teeth.¹⁸ It is essential to know methods and techniques that result in minimum or no adverse effects on roots of teeth and periodontal health. This will help the clinicians to choose the best method that will result in a faster and more physiological closure of extraction spaces. Moreover, to the best of our knowledge, limited studies have compared the effects of Ni-Ti closed-coil springs and elastomeric power chains on canine root resorption, gingival health and plaque accumulation.^{8,17,22} It is necessary to establish a comparison between these methods, as it can help clinicians to provide better care and enhance the overall effectiveness of orthodontic treatment.

OBJECTIVE:

Primary Objective: The objective of this study is to compare the canine retraction rate (in mm with a 100 mm marked scale) using Ni-Ti closed-coil springs versus elastomeric power chains during canine retraction in subjects with first premolar extractions over a period of three months. **Secondary Objective:** This study will also include an assessment of canine root resorption (in mm using periapical radiograph), dental plaque accumulation and gingival health (according to indices mentioned below with CPI-TN probe) using Ni-Ti closed-coil springs versus elastomeric power chains during canine retraction in subjects with first premolar extractions over a period of three months.

HYPOTHESIS:

Null Hypothesis: There is no significant difference between Ni-Ti closed-coil spring and elastomeric power chain on the canine root resorption, retraction rate, dental plaque accumulation and gingival health in subjects with first premolar extractions.

Alternate Hypothesis: There is a significant difference between Ni-Ti closed-coil spring and elastomeric power chain on the canine root resorption, retraction rate, dental plaque accumulation and gingival health in subjects with first premolar extractions.

OPERATIONAL DEFINITIONS:

Ni-Ti Closed-coil Spring:¹⁹ (Annexure A)

Ni-Ti closed-coil spring is a passive compressed spring made up of super elastic Nickel-titanium. Two eyelets are attached to each side of the coil to facilitate its application. The eyelets will be engaged in the hooks of the second premolar and canine brackets and will apply a force of 150 gm.

Elastomeric Power Chain:²⁰ (Annexure B)

Elastomeric power chains are resilient and latex-free orthodontic materials. They are made up of elastic material and consist of many connected rings. Each ring is engaged in a bracket to apply a force of 175-300 gm.

Plaque Index:¹⁷ (Annexure C)

Plaque index is a grading system used to assess the amount of plaque present at the gingival margins and helps in assessing oral health. It consists of four grades including, Grade 0, 1, 2 and 3. The increase in grade indicates the increased amount of plaque along the gingiva.

Gingival Index:²¹ (Annexure D)

Gingival index is a grading system that is used to assess the health of the gingiva. It consists of four grades including, Grade 0, 1, 2 and 3. The increase in grade indicates the compromised gingival health of the teeth.

Root Resorption:²²

Root resorption is a decrease in root length and width due to an inflammatory process. In orthodontics, during tooth movement, areas of necrosis develop called hyalinized areas, which result in root resorption. Periapical radiographs will be taken to assess the amount of root resorption by determining the length of the tooth from the cusp tip to the root apex.

Retraction Rate:¹⁶

The retraction rate of canine will be the distance travelled divided by the time interval needed for closure of spaces. It will be noted at four-time intervals i.e at the start of the canine retraction (T_0), after first month (T_1), second month (T_2) and third month follow-up (T_3).

Split-mouth Study:

A randomized controlled trial in which intervention and control are randomly allocated to the different quadrants in the oral cavity. In our study, Ni-Ti closed-coil springs and elastomeric power chains will be randomly allocated to the right and left quadrants of maxillary and mandibular arches.

MATERIAL & METHODS:

Study Design: A single center open labelled parallel split-mouth randomized controlled trialSettings: Dental clinics, Department of Surgery, The Aga Khan University Hospital, Karachi, Pakistan

Study Duration: One year after ethical review committee (ERC) approval **Sampling Technique:** Non-probability consecutive sampling

SAMPLE SIZE:

The sample size was calculated using standard estimate where n = 8(CV2) /(PC2) [1+(1-PC)2] where PC is the proportionate change in means (PC = $(\mu 0 - \mu 1)/\mu 0$) and CV is the coefficient of variation (CV = $\sigma 0/\mu 0 = \sigma 1/\mu 1$). The study required a minimum sample size of 33 (N) patients in each group. With an inflation of 40% for an estimated loss to follow up/non-response rate, we will be including 46 (N) participants in this study, to achieve 80% power and to detect at least a 39% change in mean canine retraction rate values of 3.88 ± 2.66 mm and 5.45 ± 1.53 mm, with

elastomeric power chains and Ni-Ti closed-coil springs, respectively⁸ and 68% or less change in coefficient of variation at two-sided 5% level of significance.

SAMPLE SELECTION:

Inclusion Criteria:

- Patients aged between 13 40 years
- Patients undergoing fixed orthodontic treatment
- Patients requiring all first premolars extraction as part of orthodontic treatment
- Patients with all permanent teeth present and erupted (except for second and third molars)
- All patients who will sign the informed consent/assent form

Exclusion Criteria:

- Patients with systemic diseases that can affect tooth movements
- Patients with uncontrolled periodontal disease
- Patients with craniofacial syndromes
- Pregnant or lactating mothers
- Patients with bracket failures greater than three times per bracket during the study
- Patients on medications that can affect tooth movements
- Patients with Nickel allergy

DATA COLLECTION PROCEDURE:

After obtaining an approval from the Ethical Review Committee and taking informed consent and informed assent from the parents and child respectively, (Annexure E, F and G), these patients will be recruited in the study as participants. Patients visiting the orthodontic clinic at the Aga Khan University Hospital Karachi will be included in this study. Detailed information regarding the study will be provided to the participants and they will be given the choice to either accept or refuse their inclusion in the study. After the extraction of all first premolars under local anesthesia, 0.018" stainless steel archwires will be inserted in the maxillary and mandibular arches. For canine retraction, Ni-Ti closed-coil springs and elastomeric power chains will be randomly allocated to the right and left quadrants of both arches. Radiographic measurement (root resorption) and clinical measurements (canine retraction, plaque accumulation and gingival health) will be

recorded at four points in time. First, at the start of the canine retraction (T_0), after first month (T_1), second month (T_2) and third month follow-up (T_3). Canine retraction rate will be recorded by using a 100 mm marked scale.¹⁶ Data will be collected on an organized study proforma (Annexure H).

Ethical Considerations:

This study will be carried out as per the guidelines of the World Medical Association's Declaration of Helsinki.²³ and the principles of Good Clinical Practice (GCP). Any modifications in the protocol will be re-submitted to the ERC. The study will be conducted in compliance with regulations and a copy of the final study protocol will be submitted to ERC. All the recorded data of patients will remain confidential. Access will be provided to no one except the investigators. Participants' names and identities will remain undisclosed; however, data may be seen by ERC or any local regulatory body. Data will be saved for 7 years as per GCP and institutional guidelines.

Randomization:

Randomization will be used in the study to allot one of the two treatment methods used for canine retraction to each side of the mouth to minimize bias and to account for individual variability. By randomly assigning different retraction methods to each side of the mouth any individual-specific factors that may affect the treatment outcomes (oral hygiene habits, masticatory habits) are likely to be equally distributed across the treatment group. Block randomization will be performed to code the type of retraction method in this trial and to determine the sequence of its administration to each participant. This will be controlled by a research faculty member of the Section of Dentistry at AKUH.

Sequence Generation:

In this two-armed study, four-blocks, each with a block size of six-possible allocation sequences for treatment arms will be generated.

(1) AABB, (2) BBAA, (3) ABAB, (4) BABA, (5) ABBA, (6) BAAB

The blocks to be utilized and their order will be determined by the research faculty member using sealed envelopeTM online software.²⁴

Allocation Sequence Concealment:

After fulfilling the inclusion criteria and obtaining consent, the patient will be recruited in the study. During the recruitment of the participants in the trial, the sealed envelope for a participant will be opened by the enrolling team member and will be allotted an intervention according to the ascending order sequence already generated by the principal investigator who is also a biostatistician.

Enrollment:

After obtaining approval from the ERC (AKUH), each participant fulfilling the inclusion criteria for the study and consenting to participate in the trial will be assigned a participant ID.

Blinding:

The study investigators, patients recruited, and assessors will not be blinded during the trial. All the measurements will be recorded by the co-investigator on the study proforma (Annexure H).

POSSIBLE RISKS OR BENEFITS:

Nickel is a known allergen, though people with nickel allergy tolerate stainless steel brackets and wires quite satisfactorily.²⁵ However, in case of any adverse events such as allergic reaction to Ni-Ti closed-coil spring such as contact dermatitis, rash, bumps, redness or irritation of the skin or mucosa, its use will be stopped, and patient will be excluded from the study.

Adverse events will be reported to ERC within a week and any serious adverse event will be reported to the Department of surgery, sponsors, CTU, DRC, and ERC within 24 hours. All emergency side effects will be managed in the emergency department and the Department of Surgery will bear the charges.

STUDY GROUPS:

The patients will be screened using the inclusion and exclusion criteria by the co-investigator. Measurements for the canine root resorption, retraction rate, plaque accumulation and gingival health will be taken at T_0 , T_1 , T_2 and T_3 .

Intervention: Ni-Ti closed-coil springs **Control:** Elastomeric power chains

The participants will receive routine instructions for oral hygiene maintenance and care of the appliance verbally.

MATERIAL STORAGE:

Ni-ti closed-coil springs and Elastomeric power chains will be stored at room temperature at the Department of Surgery, Dental inventory.

DATA ANALYSIS:

Data will be entered and analyzed in SPSS for Windows (version 23.0, SPSS Inc. Chicago). Frequencies and proportions will be reported for categorical variables, such as gender. Shapiro-Wilk test will be used to check the normality of the data. Descriptive statistics, such as means and standard deviations for normally distributed or median and interquartile range (IQR) for non-normally distributed data will be reported for all baseline clinical factors. Paired t-test will be used for the pairwise comparison. For the two groups the mean/median scores for retraction rate, root resorption, gingival health and plague accumulation between the two groups will be assessed using Independent t-test for normally distributed data and Man-Whitney U test for non-normally distributed data. A *p*-value ≤ 0.05 at 95% confidence interval will be considered as statistically significant.

On achieving 50% of the sample size, an interim analysis will be run, if the results show that the given intervention is successful in significantly improving the rate of canine retraction in patients then further trial will be stopped and all the participants will be given the intervention.

FINANCE:

Departmental funds from the Department of Surgery and intramural grants will be applied for.

PUBLISHING POLICY/PLAN:

For publication the data will be utilized, and it could be presented in either national or worldwide forums.

DATA CONFIDENTIALITY:

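### Canine retraction rate, the primary measure, is divided by the time to space closure, but measurement ends at month three and no canine is followed to closure

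*Protocol*

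**What the plan says.** Retraction rate is the sole primary objective (Protocol, OBJECTIVE), so I call it the primary measure; the protocol does not use the term primary outcome. The objective gives it in mm, read from a marked scale, "during canine retraction in subjects with first premolar extractions over a period of three months".

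OPERATIONAL DEFINITIONS, Retraction Rate, contains the only definition: "The retraction rate of canine will be the distance travelled divided by the time interval needed for closure of spaces". The next sentence has the rate noted at the start of retraction and then "after first month (T_1), second month (T_2) and third month follow-up (T_3"). DATA COLLECTION PROCEDURE and STUDY GROUPS repeat this four-visit schedule, and T3 is the last measurement.

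SAMPLE SIZE plans on "mean canine retraction rate values of 3.88 ± 2.66 mm and 5.45 ± 1.53 mm", with no time window for these values.

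DATA ANALYSIS compares "the mean/median scores for retraction rate, root resorption, gingival health" and plaque between the two methods, without restricting retraction rate to spaces that have closed. It adds an interim look at half the sample: if the intervention is found to be "significantly improving the rate of canine retraction in patients then further trial will be stopped".

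**The concern.** The written denominator is a time that the schedule observes only when a space closes by T3. A canine whose space is still open at month three has a known displacement but no value of the measure as defined. In a split-mouth trial, a left-right comparison within a patient needs a value on both sides, so one open space would remove the pair under the literal rule.

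The same quantity drives the main comparison and the interim stopping rule, and the Blinding section says that investigators, patients and assessors all know the allocation. The primary measure should therefore have one computable definition before any data are examined. At present the definition, the visit schedule and the units do not describe the same quantity.

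**Working it through.** **1. The passages side by side (all Protocol).**
- OBJECTIVE: unit mm; window three months.
- OPERATIONAL DEFINITIONS, first sentence: distance per time; window ends at space closure.
- OPERATIONAL DEFINITIONS, second sentence: a value at each of T0, T1, T2 and T3.
- DATA COLLECTION PROCEDURE: same four visits; the rate is read from a 100 mm scale, which measures length only.
- STUDY GROUPS: same four visits.
- SAMPLE SIZE: unit mm; no window.
- DATA ANALYSIS: retraction rate for the comparison and for the interim rule; no unit or window.

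No visible section records a date of closure, continues measurement until closure, or says what happens if a space is open at T3. The one year under Study Duration is the length of the study, not follow-up per canine. Annexure H (the proforma) is not in the text at hand, but a form completed at T0 to T3 could not supply a later closure time.

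**2. The literal definition at each visit.** Let d1, d2 and d3 be displacement from T0 at months 1, 2 and 3, and let C be the months to closure.
- T0: no distance and no time have elapsed, so there is no rate to note.
- T1 and T2: the denominator C is not yet known unless the space has already closed.
- T3, space closed: C is known, to within the monthly spacing of visits.
- T3, space open: C exceeds 3 and is never observed, so there is no value.

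**3. Quantities compatible with the rest of the protocol.**
- (a) d3, in mm.
- (b) d3/3, in mm per month.
- (c) the increments d1, d2 − d1 and d3 − d2, whose mean is d3/3.

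All three can be computed from the planned visits. With visits exactly on time, (a) and (b) differ only by the constant 3. Reading (c) gives three results per canine instead of one. Only the literal definition leaves canines without a value.

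**4. Does changing the unit disturb the sample size?** The protocol's formula is n = 8·CV²/PC² × [1 + (1 − PC)²]. With its stated PC = 0.39 and CV = 0.68:

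n = 8 × 0.4624/0.1521 × (1 + 0.3721) = 33.37, against the stated 33.

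Now divide the planning means and SDs by 3, assuming that they are three-month distances:
- means: 3.88/3 = 1.29 and 5.45/3 = 1.82 mm per month;
- CV: (2.66/3)/(3.88/3) = 2.66/3.88 = 0.686, unchanged;
- size of the proportionate change: (1.57/3)/(3.88/3) = 1.57/3.88 = 0.405, unchanged.

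A common divisor cancels from both inputs, so the formula returns the same n in mm or mm per month. This shows only that n does not depend on the unit. It does not endorse the inputs. Nor does it cover the case where the planning values refer to a different window, since PC and CV could then differ.

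**5. Does a fixed three-month divisor suffice?** Not for a space that closes early. If closure is recorded at T2, d/3 is two thirds of d/2. If it is recorded at T1, d/3 is one third of d/1. A fixed divisor counts months in which the canine had no space left to move into and so understates the rate, probably more often on the faster side. The replacement definition should therefore cover early closure.

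**The case against.** The strongest reply is that the definition is being read in half. Its second sentence asks for a value at every visit, which makes no sense if the denominator is final closure time. The objective fixes three months, and the data-collection section schedules the measurement at the same four visits. On this view one loose clause stands against several passages that agree on the window; the intended meaning is recoverable and no data are lost. All of that stands, and it limits the seriousness of the point. It does not remove the contradiction: the clause is the only definition given, and the recoverable meaning still leaves open which of the three quantities in the working is meant. Nor is this detail that can be left to an analysis plan, because a workable definition there would contradict the protocol.

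Three stronger readings are tempting and are not supported.

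- A reader might infer that most canines, or some minimum share of left-right pairs, would have no value. Any such figure needs the travel required for closure and the window of the planning values, and the protocol gives neither. Required travel need not equal the extraction space, since the introduction itself mentions "Friction and binding of wire to the bracket slot results in slow tooth movement and anchorage loss with sliding mechanics". Assuming a small required travel such as 3 mm also contradicts the planning values read as three-month distances: a canine cannot move a mean of 3.88 or 5.45 mm if 3 mm closes its space.
- A reader might infer that the team would be forced to change the definition after seeing data. That does not follow. The measurements and the window are fixed in advance, and the wording can be corrected now.
- A reader might infer that the analysis section uses yet another quantity. It simply repeats the defined term; the visible mismatch is with the mm unit in the objective and the sample-size statement.

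**Conclusion.** The contradiction holds, with high confidence, as a matter of text: the stated denominator does not fit a schedule that ends at T3, an instruction to note the rate at each visit, or a measure expressed in mm. Under the literal rule, a space open at T3 yields no value. How many canines that would be cannot be determined from the documents, and I put no figure on it.

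This should be corrected, but it does not invalidate the trial, because the data for a sensible definition will be collected anyway. The conclusion rests on the visible text and assumes that the proforma does not provide for follow-up to closure. The statement that n is unaffected rests on the planning values referring to a window comparable with T0 to T3.

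**What to change.** - **OPERATIONAL DEFINITIONS:** replace the closure-time denominator. For every canine, the primary outcome is displacement from T0 to T3 in mm divided by the elapsed months. If closure is first recorded at an earlier visit, it is displacement to that visit divided by the months to that visit.
- **OBJECTIVE and the interim rule in DATA ANALYSIS:** name this one quantity, in mm per month.
- **SAMPLE SIZE:** state the time window of the 3.88 and 5.45 mm values. If it is comparable with T0 to T3, the formula's n of 33 is unchanged by the rescaling; if not, the inputs need to be looked at again.

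The cost is a wording amendment, re-submitted to the ethics committee as the Ethical Considerations section requires. It needs no new visits, measurements or patients. The proforma should carry an open-or-closed entry for each space at each visit if it does not already have one. One limitation remains: closure time is known only to the nearest monthly visit, so the rate for an early-closing space is approximate.

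### The 33 per group does not follow from the means and SDs quoted beside it, and the formula is for independent groups in a split-mouth trial; no shortfall in enrolment is shown

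*Protocol*

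**What the plan says.** The SAMPLE SIZE section of the Protocol gives the formula n = 8·CV²/PC² × [1 + (1 − PC)²]. It defines PC as (μ0 − μ1)/μ0 and CV as a single value shared by both groups (σ0/μ0 = σ1/μ1). It then states:

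- Result: "The study required a minimum sample size of 33 (N) patients in each group".
- Effect: the trial is to "detect at least a 39% change in mean canine retraction rate values of 3.88 ± 2.66 mm and 5.45 ± 1.53 mm", for power chains and Ni-Ti springs respectively, at 80% power.
- Variability: "68% or less change in coefficient of variation at two-sided 5% level of significance".
- Enrolment: "With an inflation of 40% for an estimated loss to follow up/non-response rate, we will be including 46 (N) participants in this study".

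The design is split-mouth. Under OPERATIONAL DEFINITIONS (Split-mouth Study), "Ni-Ti closed-coil springs and elastomeric power chains will be randomly allocated to the right and left quadrants of maxillary and mandibular arches". DATA COLLECTION PROCEDURE repeats this, and the Randomization section says the aim is to "Ni-Ti closed-coil springs and elastomeric power chains will be randomly allocated to the right and left quadrants of both arches" in effect side by side, that is, to "allot one of the two treatment methods used for canine retraction to each side of the mouth".

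DATA ANALYSIS says "Paired t-test will be used for the pairwise comparison", without saying which pairs are meant. For the two groups' scores, retraction rate included, it names the independent t-test or the Mann-Whitney U test. The document gives neither a left-right correlation nor an SD of within-patient differences.

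**The concern.** The section states a formula, the conditions for using it, its inputs and the data behind them, and these disagree in three ways.

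1. **Sign of PC.** Chains are the first group (3.88 mm) and springs the second (5.45 mm). A rise makes PC negative as defined, and the formula is not symmetric in sign, so using +0.39 changes the answer.
2. **CV.** The formula needs one common CV, and the two quoted mean-SD pairs have very different ones. The 68% is also described as a change in CV, when it is the level of the chain CV.
3. **Design.** The formula compares two independent groups of patients, but here each patient contributes to both devices.

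At stake is the 80% power statement. As written it rests on inputs that contradict the quoted data and on a design the trial does not use. Anyone who applies the section's own definitions gets about twice 33 and may wrongly conclude that the trial is half the size it should be.

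**Working it through.** **Inputs (SAMPLE SIZE).** Chain 3.88 mm, SD 2.66; spring 5.45 mm, SD 1.53; PC 39%; CV 68%; two-sided 5%; power 80%; inflation 40%. The left-right correlation r is not given and is assumed below.

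**1. Reproducing the stated figure.** With CV = 0.68 and PC = +0.39: 8 × 0.4624 / 0.1521 × (1 + 0.61²) = 24.32 × 1.3721 = 33.4, stated as 33. Then 33 × 1.4 = 46.2, stated as 46.

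**2. PC from the quoted means.** (3.88 − 5.45)/3.88 = −0.405. With 5.45 as base it is (5.45 − 3.88)/5.45 = +0.288. Neither is +0.39. A PC of +0.39 from 3.88 describes a fall to 3.88 × 0.61 = 2.37 mm.

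| CV | PC | n per group from the formula |
|---|---|---|
| 0.68 | +0.39 | 33.4 |
| 0.68 | −0.39 | 71.3 |
| 0.68 | −0.405 (or +0.288 from the other base) | 67.2 |
| 0.686 | −0.405 | 68.3 |

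**3. CV from the quoted data.** 2.66/3.88 = 0.686 and 1.53/5.45 = 0.281, so the equal-CV condition fails. A common 0.68 would put the spring SD at 0.68 × 5.45 = 3.71 mm, against the quoted 1.53 mm.

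**4. What the raw figures support, independent groups.** Difference 5.45 − 3.88 = 1.57 mm; root-mean-square SD = √[(2.66² + 1.53²)/2] = 2.17 mm. With noncentral-t power for an independent t-test, 31 per group gives 80.0% and 33 per group gives 82.5%.

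**5. What the raw figures support, paired.** SD of differences = √(2.66² + 1.53² − 2·r·2.66·1.53) = √(9.4165 − 8.1396·r), with one right-left difference per patient and noncentral-t power for a paired t-test.

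| Assumed r | SD of differences (mm) | Patients for 80% | Power with 33 | Power with 27–28 |
|---|---|---|---|---|
| 0 | 3.069 | 32 | 81% | 73–74% |
| 0.2 | 2.791 | 27 | 88% | 80–82% |
| 0.3 | 2.641 | 25 | 91% | 84–86% |
| 0.5 | 2.312 | 20 | 97% | 92–93% |

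**6. The 40%.** Read as a multiplier, as the section words it, 46 enrolled leaves 33 after a loss of 1 − 33/46 = 28%. Read as the expected loss, 46 × 0.6 = 27.6, so 27 or 28 patients remain, which is the last column above.

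All power figures are for a fixed sample. They are not adjusted for the interim analysis at 50% of the sample that DATA ANALYSIS provides for.

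**The case against.** **The inputs are written as bounds.** The section says at least 39% and 68% or less. In size, a 40.5% rise meets the first; the spring CV of 0.281 meets the second, and the chain CV of 0.686 misses it only by rounding. This stands as a reading of the words, and the gap between 39% and 40.5% is minor. It does not rescue the derivation, because 33 still needs the wrong sign of PC and a common CV that the quoted SDs rule out.

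**The trial is large enough anyway.** This stands. A reader might infer from the 67 to 71 that the trial is about half the size it needs. The documents do not support that: those figures require a spring SD of about 3.7 mm, and the quoted value is 1.53 mm. The errors largely cancel.

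**The formula matches the test named for the group comparison.** DATA ANALYSIS does name the independent t-test or Mann-Whitney for the two groups, and the paired t-test could refer to time points. This stands, and it means that rewriting SAMPLE SIZE alone would leave the two sections in conflict. The independent test, however, does not fit the split-mouth design either.

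**Each patient may supply two pairs.** Both arches are treated, so one difference per patient may understate the information. This also stands. For illustration, if r = 0, the SDs are the same in both arches and the two arches' differences correlate at an assumed 0.5, averaging gives an SD of 3.069 × √0.75 = 2.658 mm and 25 patients suffice instead of 32. The Protocol does not say how the arches are combined.

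**The 40% is worded as an inflation.** It is, and 33 × 1.4 matches. But the sentence ties it to an estimated loss rate, so it can also be read as the expected loss. A reader might infer that the trial will end below 80% power. That follows only on the second reading, at r below about 0.2 and with one pair per patient.

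**Conclusion.** The derivation is wrong as written: the sign of PC, the common CV and the independent-groups formula each disagree with the quoted data or the design, and the 68% is mislabelled. These are errors in what the Protocol states, not detail that could be left to a statistical analysis plan.

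The number itself is not shown to be too small. On the quoted means and SDs, 80% power needs 31 per independent group or 32 patients as pairs at r = 0, and fewer at positive r, against 33 required and 46 enrolled. This rests on the 1.57 mm difference and the two SDs being taken as the Protocol gives them, on r of zero or more, on one difference per patient, and on no adjustment for the interim look. The sensitivity to r and to the loss rate is a reason to state both openly. The correction should be made, but it is a correction to the stated justification and not to the size of the trial.

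**What to change.** 1. **SAMPLE SIZE.** Delete the 39% and 68% statements. Restate the calculation for paired data with the patient as the unit: difference 1.57 mm, SD of differences = √(2.66² + 1.53² − 2·r·2.66·1.53), and r labelled as an assumption (32 patients at r = 0, 25 at r = 0.3, 20 at r = 0.5).
2. **Basis of those figures.** Say that they count one right-left difference per patient, that averaging the two arches could lower them, and that they are not adjusted for the interim look at 50%.
3. **DATA ANALYSIS.** Make the paired t-test, or the Wilcoxon signed-rank test if the differences are not normal, the between-device comparison in place of the independent t-test and Mann-Whitney, so that the two sections agree.
4. **Losses.** State that 33 × 1.4 = 46 tolerates about 28% loss. If 40% is the expected loss, state that 27 to 28 patients remain and that power on the one-pair basis is about 73–74% at r = 0 and 80–82% at r = 0.2.

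The cost is one rewritten paragraph and one changed sentence on the tests. The downside is a less favourable stated dropout tolerance or power, and a correlation that is openly assumed. The restatement does not change recruitment.
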